1.1 Synopsis

Protocol Title: A Phase 3 Open-Label Clinical Trial to Study the Immunogenicity and Safety of 9-Valent Human Papillomavirus (HPV) L1 Virus-Like Particle (VLP) Vaccine (V503) in Chinese females 9 to 45 Years of Age	
Short Title: Immunobridging study of 9vHPV vaccine in Chinese females 9 to 45 years of age	
Objectives/Hypotheses and Endpoints: This study consists of two stages, i.e. Stage I and II. The study period of Stage I is from Day 1 through Visit 10 (1 month post Dose 3) and Stage II is post Visit 10 up to Visit 15. Stage I in females 9 to 45 years of age (Day 1 to Visit 10):	
Objective/Hypothesis	Endpoint
Primary	

Objective: To demonstrate that administration of the 9-valent human papillomavirus (9vHPV) vaccine induces non-inferior geometric mean titers (GMTs) for serum anti-HPV 6, 11, 16, 18, 31, 33, 45, 52, and 58 in females 9 to 19 years of age compared to females 20 to 26 years of age. 
Hypothesis (H1): 9vHPV vaccine induces non-inferior immune responses in females 9 to 19 years of age who are seronegative at Day 1 to the relevant HPV type compared to females 20 to 26 years of age who are seronegative at Day 1 to the relevant HPV type, as measured by anti-HPV 6, 11, 16, 18, 31, 33, 45, 52, and 58 GMTs at 1 month post Dose 3. (Each vaccine component will be analyzed separately. The statistical criterion for non-inferiority requires that the lower bound of two-
	
Competitive Luminex Immunoassay (cLIA) antibody titer to each of HPV 6, 11, 16, 18, 31, 33, 45, 52, and 58.


sided 97.5% confidence interval of GMT ratio (females 9 to 19 years of age vs. females 20 to 26 years of age) be greater than 0.67 for each HPV type.)
 
 Objective: To demonstrate that administration of the 9vHPV vaccine induces non-inferior seroconversion percentages to HPV types 6, 11, 16, 18, 31, 33, 45, 52, and 58 in females 27 to 45 years of age compared to females 20 to 26 years of age. 
Hypothesis (H2): 9vHPV vaccine induces non-inferior immune responses in females 27 to 45 years of age who are seronegative at Day 1 to the relevant HPV type compared to females 20 to 26 years of age who are seronegative at Day 1 to the relevant HPV type, as measured by the seroconversion percentages to each of HPV types 6, 11, 16, 18, 31, 33, 45, 52, and 58 at 1 month post Dose 3. (Each vaccine component will be analyzed separately. The statistical criterion for non-inferiority requires that the lower bound of two-sided 97.5% confidence interval for the difference (females 27 to 45 years of age minus females 20 to 26 years of age) in seroconversion percentages be greater than -5% for each HPV type.)
	
 cLIA antibody seroconversion to each of HPV 6, 11, 16, 18, 31, 33, 45, 52, and 58.

Secondary
	

 Objective: To demonstrate that administration of the 9vHPV vaccine induces non-inferior seroconversion percentages to HPV types 6, 11, 16, 18, 31, 33, 45, 52, and 58 in females 9 to 19 years of age compared to females 20 to 26 years of age. 	
 cLIA antibody seroconversion to each of HPV 6, 11, 16, 18, 31, 33, 45, 52, and 58.


Hypothesis (H3): 9vHPV vaccine induces non-inferior immune responses in females 9 to 19 years of age who are seronegative at Day 1 to the relevant HPV type compared to females 20 to 26 years of age who are seronegative at Day 1 to the relevant HPV type, as measured by the seroconversion percentages to each of HPV types 6, 11, 16, 18, 31, 33, 45, 52, and 58 at 1 month post Dose 3. (Each vaccine component will be analyzed separately. The statistical criterion for non-inferiority requires that the lower bound of two-sided 97.5% confidence interval for the difference (females 9 to 19 years of age minus females 20 to 26 years of age) in seroconversion percentages be greater than -5% for each HPV type.)
 
• Objective: To demonstrate that administration of the 9vHPV vaccine induces non-inferior GMTs for serum anti-HPV 6, 11, 16, 18, 31, 33, 45, 52, and 58 in females 9 to 15 years of age compared to females 20 to 26 years of age. 
Hypothesis (H4): 9vHPV vaccine induces non-inferior immune responses in females 9 to 15 years of age who are seronegative at Day 1 to the relevant HPV type compared to females 20 to 26 years of age who are seronegative at Day 1 to the relevant HPV type, as measured by anti-HPV 6, 11, 16, 18, 31, 33, 45, 52, and 58 GMTs at 1 month post Dose 3. (Each vaccine component will be analyzed separately. The statistical criterion for non-inferiority requires that the lower bound of two-
	
• cLIA antibody titer to each of HPV 6, 11, 16, 18, 31, 33, 45, 52, and 58.
---	---


sided 97.5% confidence interval of GMT ratio (females 9 to 15 years of age vs. females 20 to 26 years of age) be greater than 0.67 for each HPV type.)
 
 • Objective: To summarize immune responses induced by the 9vHPV vaccine in females 9 to 15 years of age as measured by anti-HPV 6, 11, 16, 18, 31, 33, 45, 52, and 58 cLIA seroconversion percentages. • Objective: To summarize immune responses induced by the 9vHPV vaccine in females 27 to 45 years of age as measured by anti-HPV 6, 11, 16, 18, 31, 33, 45, 52, and 58 cLIA GMTs. • Objective: To summarize immune responses induced by the 9vHPV vaccine using the HPV total IgG Luminex immunoassay (IgG LIA) in females 9 to 19 years of age, 20 to 26 years of age, and 27 to 45 years of age. • Objective: To evaluate the safety of the 9vHPV vaccine in females 9 to 19 years of age, 20 to 26 years of age, and 27 to 45 years of age based on the proportions of participants experiencing solicited injection-site adverse events (AEs), solicited systemic AEs, and serious AEs. 	
 • cLIA antibody seroconversion to each of HPV 6, 11, 16, 18, 31, 33, 45, 52, and 58. • cLIA antibody titer to each of HPV 6, 11, 16, 18, 31, 33, 45, 52, and 58. • IgG LIA antibody titer and seroconversion to each of HPV 6, 11, 16, 18, 31, 33, 45, 52, and 58. • Participant experiencing solicited injection-site AEs. • Participant experiencing solicited systemic AEs. • Participant experiencing serious AEs.
---	---

Stage II in females 9 to 19 years of age (post Visit 10 to Visit 15):	
Objective/Hypothesis	Endpoint
Primary	

 Objective: To evaluate persistence of immune responses induced by the 9vHPV vaccine in females 9 to 19 years of age. 	
 cLIA antibody titer and seropositivity to each of HPV 6, 11, 16, 18, 31, 33, 45, 52, and 58. IgG LIA antibody titer and seropositivity to each of HPV 6, 11, 16, 18, 31, 33, 45, 52, and 58.
Secondary	

 Objective: To evaluate the safety of the 9vHPV vaccine in females 9 to 19 years of age based on the proportion of participants experiencing serious AEs. 	
 Participant experiencing serious AEs.
Overall Design:	
Study Phase	Phase 3
Clinical Indication	Prevention of cervical, vulvar, vaginal, and anal cancers and related precancers, anogenital lesions, Pap test abnormalities, and persistent infection caused by human papillomavirus (HPV) 6, 11, 16, 18, 31, 33, 45, 52, and 58.
Population	Healthy Chinese females 9-45 years of age will be enrolled in this study.
Study Type	Interventional
Type of Design	Multi-site, Single-arm
Type of Control	No treatment control
Study Blinding	Unblinded Open-label
Estimated Duration of Study	The Sponsor estimates that the study will require approximately 66 months from the time the first participant signs the informed consent/assent until the last participant's last study-related telephone call or visit.

Number of Participants:

Approximately 1990 participants will be enrolled in the Stage I as described in Section 9.9. Participants 9 to 19 years of age who are enrolled in the Stage I and have received 3 doses of study vaccination will be eligible for participation into the Stage II.

Treatment Groups and Duration:

Treatment Groups	All enrolled participants will intramuscularly receive a 3-dose regimen of 9vHPV vaccine (V503) at Visit 1, Visit 4, and Visit 8.
Duration of Participation	
A subset of 25 girls 9 to 15 years of age enrolled in Stage I will receive 2 doses of 9vHPV vaccine and be evaluated for safety from 1st dose through Day 15 following 2nd dose by a Data Monitoring Committee (DMC). If safety evaluation is favorable, the 25 girls evaluated for safety will receive a 3rd dose and enrollment of the rest of the participants 9 to 15 years of age will be initiated; participants 9 to 15 years of age will receive 3 doses of 9vHPV vaccine and will be followed up to 1 month post Dose 3 (Visit 10) during Stage I.
 
Participants 16 to 45 years of age will be receiving 3 doses of 9vHPV vaccine and will be followed up to Visit 10 during Stage I.
 
After Visit 10, only participants 9 to 19 years of age who have received 3 doses of study vaccination will be eligible for participation into Stage II and will be followed up to Visit 15.

[figure not shown]
Study Governance:

Study Governance Committees	Committee	Included in this study?
	Steering Committee	N
	Executive Oversight Committee	Y
	Data Monitoring Committee	Y
	Clinical Adjudication Committee	N
Study governance considerations are outlined in Appendix 1.		

A list of abbreviations used in this document can be found in Appendix 5.

1.2 Schema

The study design is depicted in [Figure 1](#).

*: Visit 6 (Month 2.5) is only applicable to the first 25 participants enrolled in the 9-15 years old group who will be evaluated for safety from 1st dose through Day 15 following 2nd dose by the Data Monitoring Committee (DMC). If safety evaluation is favorable, the 25 girls evaluated for safety will receive the 3rd dose and enrollment of the rest of participants 9 to 15 years of age will be initiated.

Figure 1 Study Diagram

1.3 Schedule of Activities (SoA)

Study Period	Stage I (Participants 9-45 years of age)										Stage II (Participants 9-19 years of age)					Notes
Visit Number/Title	Visit 1 Day 1	Visit 2 Day 9	Visit 3 Month h 1	Visit 4 Month h 2	Visit 5 Day 70	Visit 6 Month h 2.5*	Visit 7 Month h 3	Visit 8 Month h 6	Visit 9 Day 192	Visit 10 Month 7	Visit 11 Month 12	Visit 12 Month 24	Visit 13 Month 36	Visit 14 Month 48	Visit 15 Month 60	
Scheduled Day	1	9	32	62	70	77	93	184	8 days post Visit 8	31 days post Visit 8	183 days post Visit 8	548 days post Visit 8	913 days post Visit 8	1278 days post Visit 8	1643 days post Visit 8	
Scheduling Windows	± 0 day	8 to 14 days after Dose 1	31 to 38 days after Dose 1	40 to 82 days after Dose 1	8 to 14 days after Dose 2	15 to 17 days after Dose 2	31 to 38 days after Dose 2	155 to 364 days after Dose 1	8 to 14 days after Dose 3	21 to 49 days after Dose 3	± 28 days	± 28 days	± 28 days	± 28 days	± 28 days	
Administrative and General Procedures																
Informed Consent/ Assent	X															The interval between the date of consent/assent and the date of the Day 1 visit should be no more than 14 days apart. If the interval is 15 days or longer, then the participant must be re-consented.
Provide Participant Identification Card	X															
Assign Screening Number	X															
Review Inclusion/ Exclusion Criteria	X															

Study Period	Stage I (Participants 9-45 years of age)										Stage II (Participants 9-19 years of age)					Notes
Visit Number/Title	Visit 1 Day 1	Visit 2 Day 9	Visit 3 Month 1	Visit 4 Month 2	Visit 5 Day 70	Visit 6 Month 2.5*	Visit 7 Month 3	Visit 8 Month 6	Visit 9 Day 192	Visit 10 Month 7	Visit 11 Month 12	Visit 12 Month 24	Visit 13 Month 36	Visit 14 Month 48	Visit 15 Month 60	
Scheduled Day	1	9	32	62	70	77	93	184	8 days post Visit 8	31 days post Visit 8	183 days post Visit 8	548 days post Visit 8	913 days post Visit 8	1278 days post Visit 8	1643 days post Visit 8	
Scheduling Windows	± 0 day	8 to 14 days after Dose 1	31 to 38 days after Dose 1	40 to 82 days after Dose 1	8 to 14 days after Dose 2	15 to 17 days after Dose 2	31 to 38 days after Dose 2	155 to 364 days after Dose 1	8 to 14 days after Dose 3	21 to 49 days after Dose 3	± 28 days	± 28 days	± 28 days	± 28 days	± 28 days	
Review Medical History	X															
Record Medications and Non-study Vaccinations	X		X	X		X	X	X		X						
Physical Examination	X					X										Height and weight are only to be measured at Day 1.
Urine or Serum Pregnancy Testing in Participant of Childbearing Potential	X			X				X								The pregnancy testing must be sensitive to 25 mIU/mL β-hCG. Results should be negative prior to each vaccination.

Study Period	Stage I (Participants 9-45 years of age)										Stage II (Participants 9-19 years of age)					Notes
Visit Number/Title	Visit 1 Day 1	Visit 2 Day 9	Visit 3 Month 1	Visit 4 Month 2	Visit 5 Day 70	Visit 6 Month 2.5*	Visit 7 Month 3	Visit 8 Month 6	Visit 9 Day 192	Visit 10 Month 7	Visit 11 Month 12	Visit 12 Month 24	Visit 13 Month 36	Visit 14 Month 48	Visit 15 Month 60	
Scheduled Day	1	9	32	62	70	77	93	184	8 days post Visit 8	31 days post Visit 8	183 days post Visit 8	548 days post Visit 8	913 days post Visit 8	1278 days post Visit 8	1643 days post Visit 8	
Scheduling Windows	± 0 day	8 to 14 days after Dose 1	31 to 38 days after Dose 1	40 to 82 days after Dose 1	8 to 14 days after Dose 2	15 to 17 days after Dose 2	31 to 38 days after Dose 2	155 to 364 days after Dose 1	8 to 14 days after Dose 3	21 to 49 days after Dose 3	± 28 days	± 28 days	± 28 days	± 28 days	± 28 days	
Axillary Temperature and Blood Pressure Prior to Study Vaccination	X			X				X								Axillary temperature and blood pressure are taken prior to each vaccination. If the participant has a fever (defined as an axillary temperature $\geq 37.1^{\circ}\text{C}$) within the 24-hour period prior to vaccination, the vaccination should be rescheduled after the fever has resolved.
Assign Treatment/Randomization Number	X															The treatment/randomization number will be assigned by an interactive response technology (IRT) system.
Study Vaccine Administration	X			X				X								All the study-related procedures for Day 1 visit except informed consent/assent, screening number assignment, participant identification card, should be performed on the same day as and prior to the first vaccination. All 3 doses should be administered within 1 year. The interval between Dose 2 and Dose 3 should be at least 3 months.

Study Period	Stage I (Participants 9-45 years of age)										Stage II (Participants 9-19 years of age)					Notes
Visit Number/Title	Visit 1 Day 1	Visit 2 Day 9	Visit 3 Month 1	Visit 4 Month 2	Visit 5 Day 70	Visit 6 Month 2.5*	Visit 7 Month 3	Visit 8 Month 6	Visit 9 Day 192	Visit 10 Month 7	Visit 11 Month 12	Visit 12 Month 24	Visit 13 Month 36	Visit 14 Month 48	Visit 15 Month 60	
Scheduled Day	1	9	32	62	70	77	93	184	8 days post Visit 8	31 days post Visit 8	183 days post Visit 8	548 days post Visit 8	913 days post Visit 8	1278 days post Visit 8	1643 days post Visit 8	
Scheduling Windows	± 0 day	8 to 14 days after Dose 1	31 to 38 days after Dose 1	40 to 82 days after Dose 1	8 to 14 days after Dose 2	15 to 17 days after Dose 2	31 to 38 days after Dose 2	155 to 364 days after Dose 1	8 to 14 days after Dose 3	21 to 49 days after Dose 3	± 28 days	± 28 days	± 28 days	± 28 days	± 28 days	
Immunogenicity Procedures																
Blood Collection	X									X	X	X	X	X	X	The blood sample collected at Day 1 for anti-HPV antibody measurements must be collected before vaccination.
Safety Procedures																
30-minute Post-Vaccination Observation	X			X				X								
Provide Vaccination Report Card (VRC)	X			X				X								

Study Period	Stage I (Participants 9-45 years of age)										Stage II (Participants 9-19 years of age)					Notes
Visit Number/Title	Visit 1 Day 1	Visit 2 Day 9	Visit 3 Month 1	Visit 4 Month 2	Visit 5 Day 70	Visit 6 Month 2.5*	Visit 7 Month 3	Visit 8 Month 6	Visit 9 Day 192	Visit 10 Month 7	Visit 11 Month 12	Visit 12 Month 24	Visit 13 Month 36	Visit 14 Month 48	Visit 15 Month 60	
Scheduled Day	1	9	32	62	70	77	93	184	8 days post Visit 8	31 days post Visit 8	183 days post Visit 8	548 days post Visit 8	913 days post Visit 8	1278 days post Visit 8	1643 days post Visit 8	
Scheduling Windows	± 0 day	8 to 14 days after Dose 1	31 to 38 days after Dose 1	40 to 82 days after Dose 1	8 to 14 days after Dose 2	15 to 17 days after Dose 2	31 to 38 days after Dose 2	155 to 364 days after Dose 1	8 to 14 days after Dose 3	21 to 49 days after Dose 3	± 28 days	± 28 days	± 28 days	± 28 days	± 28 days	
Review and Collect VRC data		X	X		X	X	X		X	X						
Collect New Medical Conditions			X	X			X	X		X	X	X	X	X	X	After Day 1, any new medical conditions not already recorded as medical history or adverse events are collected.
Clinical Follow-up for Safety	X	X	X	X	X	X	X	X	X	X	X	X	X	X	X	Review and follow AEs, SAEs and other reportable safety events. See Section 8.4.1 for time period and frequency of safety events reporting during the study.

*: Visit 6 (Month 2.5) is only applicable to a subset of participants aged 9-15 years (N=25) who will be evaluated for safety from the 1st dose through Day 15 following the 2nd dose by the Data Monitoring Committee (DMC). If the safety is favorable, this subset of participant will receive the 3rd dose and enrollment of the rest of participants in the 9-15 years old group will be initiated.

2. Introduction

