The safety will be monitored for all participants from Day 1 through Visit 10. Vaccination Report Card (VRC) will be provided to each participant after vaccination for recording AE information within 30 days (Days 1-31) after study vaccination including the day of vaccination. Serious adverse events (SAEs), cancers, overdoses, pregnancy events, lactation events, and SAEs of infants born to participant who received the study vaccine or who were breastfed during the vaccination period will be collected during the entire period of Stage I.

As participants 20-45 years of age will not enter into Stage II, the last study visit for these participants will be the Visit 10.

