8.3.1 Vaccination Report Card and Patient Reported Outcome

All participants will receive a VRC at each study vaccination visit (Visit 1, Visit 4, and Visit 8).

Using the VRC, participant or participant's legally acceptable representative will be asked to record the following safety information: axillary temperature in the evening after each study vaccination and daily, at the same time of day whenever possible, for 7 days after each study vaccination; solicited injection-site AEs (injection-site redness, swelling, induration, and pain) from Day 1 through Day 8 after each study vaccination; any AEs from Day 1 through Day 31 after each study vaccination. Participant or participant's legally acceptable representative will be asked to record concomitant medications and concomitant vaccinations for 15 days following each study vaccination on VRC. Medications taken by participants due to AEs during Day 16 through Day 31 after each study vaccination will also be collected on VRC.

VRCs will be returned for review on Day 9 (i.e. Visit 2, Visit 5, and Visit 9) and Day 32 (i.e. Visit 3, Visit 7, and Visit 10) after each study vaccination, respectively. The first 25 participants enrolled in the 9-15 years old group will have an additional VRC return visit (Visit 6) to collect the safety data through Day 15 following the 2nd dose.

Except Visit 10 (1 month post Dose 3) at which visit blood samples will be collected, the purpose of other VRC return visits is to review the VRCs, so out of windows will not be considered as protocol deviation for Visit 2, Visit 3, Visit 5, Visit 6, Visit 7, and Visit 9. However, Visit 10 sample collection out of windows will be considered as a protocol deviation.

Telephone contacts will be done around every week between Visit 2 and Visit 3, Visit 5 and Visit 7 (telephone contacts will be done after Visit 6 for the first 25 participants in the 9-15 years old group), Visit 9 and Visit 10 until the VRCs are returned to remind the participants to record the VRC and answer any questions related to VRC.

SAEs, cancers, overdoses, pregnancy events, lactation events, and infant SAEs will be collected during the entire study period as instructed in the Section 8.4.

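### The Visit 10 window opens 21 days after Dose 3, so a compliant visit can close the report card before the 30-day AE period has ended

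*Combined protocol and SAP*

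**What the plan says.** Section 4.1.1 provides the report card "for recording AE information within 30 days (Days 1-31) after study vaccination including the day of vaccination". Section 8.4.1 sets the matching reporting duty: all AEs from each vaccination through 30 days afterwards.

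Section 8.3.1 has the card returned at "Day 32 (i.e. Visit 3, Visit 7, and Visit 10) after each study vaccination". In the Schedule of Activities (Section 1.3) the three visits have the same nominal timing but different windows:

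- Visit 3: "31 to 38 days after Dose 1"
- Visit 7: "31 to 38 days after Dose 2"
- Visit 10: scheduled "31 days post Visit 8", with a window of "21 to 49 days after Dose 3"

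Visit 10 is also the post-Dose 3 serum visit, and its window is the PPI sampling criterion in Section 9.5.1. Under Section 8.3.1 only sampling outside that window counts as a deviation. The same section runs roughly weekly reminder calls between Visit 9 and Visit 10, until the card is returned.

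For ages 20-45, Section 4.1.1 states that "the last study visit for these participants will be the Visit 10". Section 4.1.2 says the same of those aged 9-19 who do not enter Stage II. Section 8.4.1 adds that investigators need not actively look for events in people who have left the study.

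**The concern.** One visit serves two purposes with different timing needs. The serum sample can be taken anywhere in a four-week range. The report card can be closed only when the AE period is over. For Doses 1 and 2 the return window opens after that period has closed. For Dose 3 it opens well before.

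A participant seen at 21 days has complied fully, and nothing would be flagged. If her card is taken then and she has no later visit or call, no written procedure captures an AE that starts in the rest of the period.

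Systemic AEs from Day 1 through Day 31 after any vaccination are a key safety endpoint in Section 9.4.2, and Table 5 carries several rows on the same 30-day period, including severe events. A participant with a shortened Dose 3 card stays in the APaT denominator (Section 9.5.2), while her late events cannot reach the numerator. Section 9.6.2 gives no rule for incomplete cards.

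**Working it through.** This is calendar arithmetic; no power or sample-size formula applies.

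**Inputs**
- AE period: Days 1-31 with the vaccination day as Day 1, which is 0 to 30 days after the dose (Sections 4.1.1, 8.3.1, 8.4.1).
- Scheduled days and windows: Section 1.3.
- Planned numbers: 690 aged 9-19, 650 aged 20-26, 650 aged 27-45 (Section 4.1.1).

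**Reproducing the Day 32 return**
- Visit 3: 32 − 1 = 31 days after Dose 1.
- Visit 7: 93 − 62 = 31 days after Dose 2.
- Visit 10: 31 days after Visit 8, when Dose 3 is given.

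In each case 31 days after the dose is Day 32, so Section 8.3.1 agrees with the nominal schedule. The conflict lies only in the Visit 10 window.

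**Diary days left uncovered by a visit t days after the dose**

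Uncovered days = max(0, 30 − t), counting the visit day itself as covered.

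| Visit day t | Uncovered days | Share of 31 |
|---|---|---|
| 21 | 9 | 29% |
| 25 | 5 | 16% |
| 29 | 1 | 3% |
| 30 | 0 | 0% |
| 31 | 0 | 0% |

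At t = 21 the uncovered days are 22 to 30 after the dose (Days 23-31).

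**Permitted visit days that fall short**
- Visits 3 and 7: 38 − 31 + 1 = 8 permitted days each; 0 of 8 fall short.
- Visit 10: 49 − 21 + 1 = 29 permitted days; days 21 to 29 fall short, which is 9/29 = 31%.

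**Who has no later visit**
- By design, 650 + 650 = 1300 of 1990 (65%), plus any aged 9-19 who do not enter Stage II.
- Stage II entrants also hand in the Dose 3 card at Visit 10. Their non-serious AEs on the uncovered days can be missed too, although SAEs and the other events listed in Section 4.1.2 continue to be collected.

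**Weight over the regimen**
- Worst case for one participant: 9 of 3 × 31 = 93 diary days, about 10%. The endpoint counts participants with an event after any dose, so a participant is lost from it only if her sole qualifying events fall on the uncovered days.

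**The case against.** The strongest reply is that the collection period is fixed independently of the visit date. Section 8.4.1 obliges the investigator to report all AEs through 30 days after any dose. Section 8.3.1 tells the participant to record through Day 31. The card is also brought back for review at Day 9, so a return visit does not in itself stop recording. On this view an early blood draw cancels nothing, and only a sentence on close-out is missing. It stands that the period is specified. But nothing puts it into effect after Visit 10 for a participant who has left: no later contact is scheduled, the calls are placed before Visit 10, and active follow-up of former participants is not required.

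It also stands that the effect is bounded. The nominal visit is late enough, only early attendees are exposed, solicited AEs are complete by Day 8, and safety is descriptive with within-group intervals.

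A reader might infer more than the documents support in three ways:
- **Ten lost days.** Counting permitted visit days before the 31-day opening of Visits 3 and 7 gives 10 of 29. But a visit at 30 days falls on the last AE day, so whole days are lost only on visit days 21 to 29, and at most 9 diary days go uncovered.
- **Bias between age groups in systemic AEs.** Only ages 9-19 can have later visits, but the Dose 3 card is collected at Visit 10 in every age group. Any difference is therefore confined to SAEs and the other events still collected in Stage II.
- **A certain loss in 1300 participants.** That is the number for whom Visit 10 is the last visit, not the number who will attend early.

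**Conclusion.** The window contradicts the AE period that the plan itself sets. A fully compliant Visit 10 on days 21 to 29 can leave between 1 and 9 of the 31 Dose 3 diary days without a collection procedure.

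The exposed results are the Day 1-31 systemic AE proportions and the related Table 5 rows, where missed events can only lower the figures. SAEs arising on those days in participants who have left are also exposed. Solicited Day 1-8 AEs and H1-H4 are untouched.

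This rests on two assumptions: that the card is handed in for good at Visit 10, as Section 8.3.1 reads, and that sites make no contact beyond those written down. The documents do not say how many participants would attend before day 30. The possible range is none to all, so the size of any understatement cannot be calculated.

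**What to change.** Keep 21 to 49 days as the serum window and PPI criterion. Reconcile the Schedule of Activities and Section 8.3.1 with Section 8.4.1 by separating report-card close-out from the blood draw. Where Visit 10 falls before the protocol's own 30-day AE period is complete, the participant keeps the card, and it is collected or completed by telephone once that period has ended. This brings the uncovered days to 0 for participants who are reached, as already holds for in-window Visits 3 and 7.

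The cost is one extra telephone contact per early attendee, plus wording in two sections. Reminder calls are already in use, and Section 8.1.12 already accepts a telephone call for the final assessment of participants who withdraw. The immunogenicity analysis does not change.
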